10.2 Adverse Events of Special Interest (AESI)

An adverse event of special interest (AESI) is one of scientific and medical interest specific to understanding of the Investigational Product and may require close monitoring and rapid communication by the investigator to the sponsor. An AESI may be serious or non-serious. The rapid reporting of AESIs allows ongoing surveillance of these events in order to characterize and understand them in association with the use of this investigational product.

10.2.1 Durvalumab + Tremelimumab AESIs

AESIs for durvalumab and tremelimumab include but are not limited to events with a potential inflammatory or immune-mediated mechanism and which may require more frequent monitoring and/or interventions such as steroids, immunosuppressants and/or hormone replacement therapy. These AESIs are being closely monitored in clinical studies with durvalumab monotherapy and combination therapy. An immune-related adverse event (irAE) is defined as an adverse event that is associated with drug exposure and is consistent with an immune-mediated mechanism of action and where there is no clear alternate etiology. Serologic, immunologic, and histologic (biopsy) data, as appropriate, should be used to support an irAE diagnosis. Appropriate efforts should be made to rule out neoplastic, infectious, metabolic, toxin, or other etiologic causes of the irAE.

If the Investigator has any questions in regard to an adverse event (AE) being an irAE, the Investigator should promptly contact the Study Sponsor.

AESIs observed with durvalumab and tremelimumab include:

- Diarrhea / Colitis and intestinal perforation
- Pneumonitis / ILD
- ALT/AST increases / hepatitis / transaminase increases / hepatotoxicity
- Neuropathy / neuromuscular toxicity (i.e. events of encephalitis, peripheral motor and sensory neuropathies, Guillain-Barré, and myasthenia gravis)
- Endocrinopathy (i.e. events of hypophysitis / hypopituitarism, adrenal insufficiency, and hyper- and hypothyroidism and type I diabetes mellitus)

- Rash / Dermatitis
- Nephritis / Blood creatinine increases
- Pancreatitis (or labs suggestive of pancreatitis - increased serum lipase, increased serum amylase)
- Myocarditis
- Myositis / Polymyositis
- Intestinal Perforation
- Other inflammatory responses that are rare / less frequent with a potential immune-mediated etiology include, but are not limited to, pericarditis, sarcoidosis, uveitis and other events involving the eye (e.g., keratitis and optic neuritis) skin (e.g., scleroderma, vitiligo and pemphigoid) , hematological (e.g., hematological anemia and immune thrombocytopenic purpura) and rheumatological events (polymyalgia rheumatic and autoimmune arthritis), vasculitis, non-infectious meningitis and non-infectious encephalitis.

Further information on these risks (e.g. presenting symptoms) can be found in the current version of the durvalumab and tremelimumab Investigator Brochure. For durvalumab and tremelimumab, AESIs will comprise the following:

Pneumonitis

AEs of pneumonitis are also of interest for AstraZeneca, as pneumonitis has been observed with use of anti-PD-1 mAbs (but not with anti-PD-L1 mAbs). Initial work-up should include a high-resolution CT scan, ruling out infection, and pulse oximetry. Pulmonary consultation is highly recommended. Guidelines for the management of patients with immune-related AEs (irAEs) including pneumonitis are provided in Appendix G.

Infusion reactions

AEs of infusion reactions (also termed infusion-related reactions) are of special interest to AstraZeneca and are defined, for the purpose of this protocol, as all AEs occurring from the start of IP infusion up to 48 hours after the infusion start time. For all infusion reactions, SAEs should be reported to AstraZeneca Patient safety as described in Section 10.4.

Hypersensitivity reactions

Hypersensitivity reactions as well as infusion-related reactions have been reported with anti-PD-L1 and anti-PD-1 therapy (45). As with the administration of any foreign protein and/or other biologic agents, reactions following the infusion of mAbs can be caused by various mechanisms, including acute anaphylactic (IgE-mediated) and anaphylactoid reactions against the mAbs and serum sickness. Acute allergic reactions may occur, may be severe, and may result in death. Acute allergic reactions may include hypotension, dyspnea, cyanosis, respiratory failure, urticaria, pruritus, angioedema, hypotonia, arthralgia, bronchospasm, wheeze, cough, dizziness, fatigue, headache, hypertension, myalgia, vomiting, and unresponsiveness. Guidelines for the management

of patients with hypersensitivity (including anaphylactic reaction) and infusion-related reactions are provided in Section 6.2.1.1.

Hepatic function abnormalities (hepatotoxicity)

Hepatic function abnormality is defined as any increase in ALT or AST to greater than $3 \times$ ULN and concurrent increase in total bilirubin to be greater than $2 \times$ ULN. Concurrent findings are those that derive from a single blood draw or from separate blood draws taken within 8 days of each other. Follow-up investigations and inquiries will be initiated promptly by the investigational site to determine whether the findings are reproducible and/or whether there is objective evidence that clearly supports causation by a disease (e.g., cholelithiasis and bile duct obstruction with distended gallbladder) or an agent other than the IP. Guidelines for management of patients with hepatic function abnormality are provided in Appendix G.

Gastrointestinal disorders

Diarrhea/colitis is the most commonly observed treatment emergent SAE when tremelimumab is used as monotherapy. In rare cases, colon perforation may occur that requires surgery (colectomy) or can lead to a fatal outcome if not properly managed. Guidelines on management of diarrhea and colitis in patients receiving tremelimumab are provided in Appendix G.

Endocrine disorders

Immune-mediated endocrinopathies include hypophysitis, adrenal insufficiency, and hyper- and hypothyroidism. Guidelines for the management of patients with immune-mediated endocrine events are provided in Appendix G.

Pancreatic disorders

Immune-mediated pancreatitis includes autoimmune pancreatitis, and lipase and amylase elevation. Guidelines for the management of patients with immune-mediated pancreatic disorders are provided in Appendix G.

Neurotoxicity

Immune-mediated nervous system events include encephalitis, peripheral motor and sensory neuropathies, Guillain-Barré, and myasthenia gravis. Guidelines for the management of patients with immune-mediated neurotoxic events are provided in Appendix G.

Nephritis

Consult with Nephrologist. Monitor for signs and symptoms that may be related to changes in renal function (e.g. routine urinalysis, elevated serum BUN and creatinine, decreased creatinine clearance, electrolyte imbalance, decrease in urine output, proteinuria, etc.).

Patients should be thoroughly evaluated to rule out any alternative etiology (e.g., disease progression, infections etc.).

Steroids should be considered in the absence of clear alternative etiology even for low grade events (Grade 2), in order to prevent potential progression to higher grade event. Guidelines for the management of patients with immune-mediated neurotoxic events are provided in Appendix G.

10.2.2 Olaparib Adverse Events of Special Interest (AESIs)

Adverse Events of Special Interest (AESIs) for olaparib are the Important Potential Risks of MDS/AML, new primary malignancy (other than MDS/AML) and pneumonitis.

ANY event of MDS/AML, new primary malignancy, or pneumonitis should be reported to AstraZeneca Patient Safety whether it is considered a non-serious AE [e.g. non-melanoma skin cancer] or SAE, and regardless of investigator's assessment of causality or knowledge of the treatment arm.

A questionnaire will be sent to any investigator reporting an AESI, as an aid to provide further detailed information on the event. During the study there may be other events identified as AESIs that require the use of a questionnaire to help characterize the event and gain a better understanding regarding the relationship between the event and study treatment.

10.2.3 Immune-related Adverse Events

Based on the mechanism of action of durvalumab and tremelimumab leading to T-cell activation and proliferation, there is a possibility of observing irAEs during the conduct of this study. Potential irAEs may be similar to those seen with the use of ipilimumab, BMS-936558 (anti-PD-1 mAb), and BMS-936559 (anti-PD-L1 mAb) and may include immune-mediated enterocolitis, dermatitis, hepatitis (hepatotoxicity), pneumonitis, and endocrinopathies (23, 45, 56) These AEs are inflammatory in nature and can affect any organ. With anti-PD-L1 and anti-CTLA-4 combination therapy, the occurrence of overlapping or increasing cumulative toxicities that include irAEs could potentially occur at higher frequencies than with either durvalumab or tremelimumab monotherapy. Patients should be monitored for signs and symptoms of irAEs. In the absence of an alternate etiology (e.g., infection or PD), an immune-related etiology should be considered for signs or symptoms of enterocolitis, dermatitis, pneumonitis, hepatitis, and endocrinopathy. In addition to the dose modification guidelines provided in Appendix G – Table A), it is recommended that irAEs are managed according to the general treatment guidelines outlined for ipilimumab (57). These guidelines recommend the following:

- Patients should be evaluated to identify any alternative etiology.
- In the absence of a clear alternative etiology, all events of an inflammatory nature should be considered immune related.
- Symptomatic and topical therapy should be considered for low-grade events.
- Systemic corticosteroids should be considered for a persistent low-grade event or for a severe event.
- More potent immunosuppressives should be considered for events not responding to systemic steroids (e.g., infliximab or mycophenolate).
- If the Investigator has any questions in regard to an AE being an irAE, the Investigator should immediately contact the Study Sponsor.

10.3 Serious Adverse Events

10.3.1 Definition

A serious adverse event (SAE) is any adverse event (experience) that in the opinion of either the investigator or sponsor results in **ANY** of the following:

- Death.
- A life-threatening adverse event (experience). Any AE that places a participant or participants, in the view of the Investigator or sponsor, at immediate risk of death from the reaction as it occurred. It does **NOT** include an AE that, had it occurred in a more severe form, might have caused death.
- Inpatient hospitalization or prolongation of existing hospitalization (for > 24 hours).
- A persistent or significant incapacity or substantial disruption of the ability to conduct normal life functions.
- A congenital anomaly or birth defect.
- Important Medical Event (IME) that, based upon medical judgment, may jeopardize the participant and may require medical or surgical intervention to prevent one of the outcomes listed above.
- Medical or scientific judgment should be exercised in deciding whether expedited reporting is appropriate in this situation. Examples of medically important events are intensive treatment in an emergency room or at home for allergic bronchospasm, blood dyscrasias, or convulsions that do not result in hospitalizations; or development of drug dependency or drug abuse.

The causality of SAEs (their relationship to all study treatment/procedures) will be assessed by the investigator(s) and communicated to AstraZeneca.

10.3.2 Reporting Serious Adverse Events

All new SAEs occurring from the date the participant signs the study consent until 90 days after the last intervention or a new treatment is started, whichever comes first, will be reported. The RPCI SAE Source Form is to be completed with all available information, including a brief narrative describing the SAE and any other relevant information.

SAEs that are unexpected and possibly, probably or definitely related must be reported as an Unanticipated Problem. Please refer to **Section 10.6** for details on reporting Unanticipated Problems.

10.4 Investigator Reporting: Notifying the Study Sponsor

All SAEs will be reported, whether or not considered causally related to the investigational product, or to the study procedure(s). The reporting period for SAEs is the period immediately following the time that written informed consent is obtained through 90 days after the last dose of durvalumab + tremelimumab + olaparib or, until the initiation of alternative anticancer therapy.

The investigator and/or Sponsor are responsible for informing the Ethics Committee and/or the Regulatory Authority of the SAE as per local requirements.

The investigator and/or sponsor must inform the FDA, via a MedWatch form, of any serious or unexpected adverse events that occur in accordance with the reporting obligations of 21 CFR 312.32, and will concurrently forward all such reports to AstraZeneca. A copy of the MedWatch report must be faxed to AstraZeneca at the time the event is reported to the FDA. It is the responsibility of the sponsor to compile all necessary information and ensure that the FDA receives a report according to the FDA reporting requirement timelines and to ensure that these reports are also submitted to AstraZeneca at the same time.

* A *cover page* should accompany the **MedWatch** form indicating the following:

- “Notification from an Investigator Sponsored Study”
- The investigator IND number assigned by the FDA
- The investigator’s name and address
- The trial name/title and AstraZeneca ISS reference number (ESR-16-11751)

* Sponsor must also indicate, either in the SAE report or the cover page, the *causality* of events *in relation to all study medications* and if the SAE is *related to disease progression*, as determined by the principal investigator.

* *Send SAE report and accompanying cover page by way of email to AstraZeneca’s designated mailbox:*

[contact]

If a non-serious AE becomes serious, this and other relevant follow-up information must also be provided to AstraZeneca and the FDA.

Serious adverse events that do not require expedited reporting to the FDA still need to be reported to AstraZeneca preferably using the MedDRA coding language for serious adverse events. This information should be reported on a monthly basis and under no circumstance less frequently than quarterly.

10.5 Follow-Up for Serious Adverse Events

All related SAEs should be followed to their resolution, until the study participant is lost to follow-up, the start of a new treatment, or until the study investigator assesses the event(s) as stable or irreversible. New information will be reported when it is received.

10.6 Unanticipated Problems

10.6.1 Definition

An Unanticipated Problem (UP) is any incident, experience, or outcome that meets all of the following criteria:

- Unexpected (in terms of nature, severity, or frequency) given:

- a) The research procedures that are described in the study-related documents, including study deviations, as well as issues related to compromise of participant privacy or confidentiality of data.
- b) The characteristics of the participant population being studied.
- Related or possibly related to participation in the research (possibly related means there is a reasonable possibility that the incident, experience, or outcome may have been caused by the procedures involved in the research).
- Suggests that the research places participants or others at a greater risk of harm (including physical, psychological, economic, or social harm) than was previously known or recognized and if in relation to an AE is also deemed **Serious** per **Section 10.3**.

10.6.2 Reporting Unanticipated Problems

The Reportable New Information (RNI) Form will be submitted to the CRS Quality Assurance (QA) Office within 1 business day of becoming aware of the Unanticipated Problem. After review, CRS QA Office will submit the RNI to the IRB.

When becoming aware of new information about an Unanticipated Problem, submit the updated information to CRS QA Office with an updated Reportable New Information Form. The site Investigator or designated research personnel will report all unanticipated problems, whether related or unrelated to the investigational agent(s) to the IRB in accordance with their local institutional guidelines.

10.7 Reporting of Deaths

All deaths that occur during the study, or within the protocol defined 90 day post last dose of durvalumab + tremelimumab + olaparib (follow up period), must be reported as follows:

- Death that is clearly the result of disease progression should be documented but should not be reported as an SAE.
- Where death is not due (or not clearly due) to progression of the disease under study, the AE causing the death must be reported to as a SAE within **24 hours** (see Section 10.3.2 for further details). The report should contain a comment regarding the co-involvement of progression of disease, if appropriate, and should assign main and contributory causes of death.
- Deaths with an unknown cause should always be reported as a SAE.

Deaths that occur following the protocol-defined 90-day post-last-dose of durvalumab + tremelimumab + olaparib follow-up period will be documented as events for survival analysis but will not be reported as an SAE.

10.8 Other Events Requiring Reporting

10.8.1 Overdose

An overdose is defined as a subject receiving a dose of durvalumab + tremelimumab + olaparib in excess of that specified in the Investigator's Brochure, unless otherwise specified in this protocol.

Any overdose of a study subject with durvalumab + tremelimumab + olaparib, with or without associated AEs/SAEs, is required to be reported within 24 hours of knowledge of the event to the sponsor and AstraZeneca/MedImmune Patient Safety or designee using the designated Safety e-mailbox (see Section 10.4 for contact information). If the overdose results in an AE, the AE must also be recorded as an AE (see Section 10.1). Overdose does not automatically make an AE serious, but if the consequences of the overdose are serious, for example death or hospitalization, the event is serious and must be recorded and reported as an SAE (see Section 10.3). There is currently no specific treatment in the event of an overdose of durvalumab or tremelimumab or olaparib.

The investigator will use clinical judgment to treat any overdose.

10.8.2 Hepatic function abnormality

Hepatic function abnormality (as defined in Section 10.2.1) in a study subject, with or without associated clinical manifestations, is required to be reported as "hepatic function abnormal" ***within 24 hours of knowledge of the event*** to the sponsor and AstraZeneca/MedImmune Patient Safety using the designated Safety e-mailbox (see Section 10.3.2 for contact information), unless a definitive underlying diagnosis for the abnormality (e.g., cholelithiasis or bile duct obstruction) that is unrelated to investigational product has been confirmed.

- If the definitive underlying diagnosis for the abnormality has been established and is unrelated to investigational product, the decision to continue dosing of the study subject will be based on the clinical judgment of the investigator.
- If no definitive underlying diagnosis for the abnormality is established, dosing of the study subject must be interrupted immediately. Follow-up investigation and inquiries must be initiated by the investigational site without delay.

Each reported event of hepatic function abnormality will be followed by the investigator and evaluated by the sponsor and AstraZeneca/MedImmune.

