
Hepatitis (elevated LFTs) Infliximab should not be used for management of immune-related hepatitis.
 
PLEASE SEE shaded area immediately below this section to find guidance for management of "Hepatitis (elevated LFTs)" in HCC patients
	
Any Elevations in AST, ALT or TB as Described Below
 
(AST or ALT $> 3 \times$ ULN if baseline normal, 1.5-3.0\timesbaseline if baseline abnormal; and/or TB $> 1.5 \times$ ULN if baseline normal, $> 1.0-1.5 \times$baseline if baseline abnormal)
 
(AST or ALT > 3 to $5 \times$ ULN if baseline normal, $> 3-5 \times$baseline if baseline abnormal; and/or TB > 1.5 to $3.0 \times$ ULN if baseline normal, $> 1.5-3.0 \times$baseline if baseline abnormal)
	
General Guidance
 
No dose modifications.
 
 If it worsens, then treat as described for elevations in the row below. 
Hold study drug/study regimen dose until resolution to AST or ALT $\leq 3.0 \times$ULN and/or TB $\leq 1.5 \times$ULN if baseline normal, or to AST or ALT $\leq 3.0 \times$baseline and/or TB $\leq 1.5 \times$baseline if baseline abnormal.
 
 If toxicity worsens, then treat as described for elevation in the row below. If toxicity improves to AST or ALT $\leq 3.0 \times$ULN and/or TB $\leq 1.5 \times$ULN if baseline normal, or to AST or ALT $\leq 3.0 \times$baseline and/or TB $\leq 1.5 \times$baseline if baseline abnormal in 1 to 2 days, consider, as necessary, discussing with study physician. 	
For Any Elevations Described:
 
 Monitor and evaluate liver function test: AST, ALT, ALP, and TB. Evaluate for alternative etiologies (e.g., viral hepatitis, disease progression, concomitant medications). 
 Continue LFT monitoring per protocol. 
 Regular and frequent checking of LFTs (e.g., every 1 to 2 days) until elevations of these are improving or resolved. If no resolution to AST or ALT $\leq 3.0 \times$ULN and/or TB $\leq 1.5 \times$ULN if baseline normal, or to AST or ALT $\leq 3.0 \times$baseline and/or TB $\leq 1.5 \times$baseline if baseline abnormal in 1 to 2 days, consider, as necessary, discussing with study physician.

Specific Immune-mediated Reactions			
Adverse Events	Severity Grade of the Event (NCI CTCAE version 4.03)	Dose Modifications	Toxicity Management

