		
abnormal, within 14 days and after completion of steroid taper.
 
 Permanently discontinue study drug/study regimen if the elevations do not downgrade as described in bullet above within 14 days 
 For elevations in transaminases $>8\times$ULN or elevations in TB $>5\times$ULN if baseline normal, or for elevations in transaminases $>8\times$baseline and/or TB $>5\times$baseline if baseline abnormal, permanently discontinue study drug/study regimen. Permanently discontinue study drug/study regimen for any case meeting Hy's law criteria (AST and/or ALT $>3\times$ULN + bilirubin $>2\times$ULN without initial findings of cholestasis (i.e., elevated alkaline P04) and in the absence of any alternative cause.^b 	treatment (refer to current NCCN guidelines for treatment of cancer-related infections). ^a

Hepatitis (elevated LFTs)
 
Infliximab should not be used for management of immune-related hepatitis
 
See instructions at bottom of shaded area if transaminase rise is not isolated but (at any time) occurs in setting
	
Elevations in AST, ALT or TB as Described Below
	
General Guidance
	
For Any Elevations Described:
 
 Monitor and evaluate liver function test: AST, ALT, ALP, and TB. Evaluate for alternative etiologies (e.g., viral hepatitis, disease progression, concomitant medications, worsening of liver cirrhosis [e.g., portal vein thrombosis]). For HBV+ patients: evaluate quantitative HBV viral load, quantitative HBsAg, or HBeAg For HCV+ patients: evaluate quantitative HCV viral load Consider consulting hepatologist/Infectious Disease specialist regarding change/implementation in/of antiviral medications for any patient with an elevated HBV viral load >2000 IU/ml Consider consulting hepatologist/Infectious Disease specialist regarding

Specific Immune-mediated Reactions			
Adverse Events	Severity Grade of the Event (NCI CTCAE version 4.03)	Dose Modifications	Toxicity Management

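### Appendix G's hepatitis rows conflict with the protocol's own Hy's law and hepatic-function-abnormality rules, and no order of precedence is stated

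*Combined protocol and SAP*

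**What the plan says.** Section 10.2.1 defines the event in multiples of ULN: "Hepatic function abnormality is defined as any increase in ALT or AST to greater than $3 \times$ ULN" with a "concurrent increase in total bilirubin to be greater than $2 \times$ ULN", on one blood draw or on draws within 8 days of each other. It then hands over management: "Guidelines for management of patients with hepatic function abnormality are provided in Appendix G".

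Section 10.8.2 applies that definition. If an unrelated diagnosis is established, continued dosing is left to the investigator's judgment. Otherwise: "If no definitive underlying diagnosis for the abnormality is established, dosing of the study subject must be interrupted immediately". Nothing is said about restart or permanent discontinuation.

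The Appendix G block on hepatitis with elevated liver function tests has three rows that apply here; the separate shaded block is limited to HCC patients. The first row makes no dose change and adds: "If it worsens, then treat as described for elevations in the row below". The second holds drug and resumes it after improvement and steroid taper. The third, headed by AST/ALT above 5×ULN and/or bilirubin above 3×ULN, splits into hold or permanent stop by level. Its cell also contains a bullet that begins "Permanently discontinue study drug/study regimen for any case meeting" Hy's law criteria, given there as AST and/or ALT above 3×ULN plus bilirubin above 2×ULN, without initial cholestasis and without an alternative cause.

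**The concern.** The Hy's law bullet uses the same numeric thresholds as Sections 10.2.1 and 10.8.2, and these lie well below the row in which it is printed. A site that looks up the row matching its laboratory values can therefore reach an instruction to resume without ever meeting the bullet that says stop for good. A second mismatch comes from the units: when baseline is abnormal, the rows switch to multiples of baseline, while the other three statements stay with multiples of ULN.

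The stake is patient safety after possible drug-induced liver injury. In a multicenter trial, identical results could also lead to different actions, which would affect exposure and discontinuation counts. For events in the first 8 weeks, it could also decide who is evaluable under Section 12.4, which requires two antibody cycles and 8 weeks of olaparib.

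**Working it through.** No sample size or error rate is involved. The check sets the printed rules side by side and sees which apply to a given result. TB is total bilirubin.

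| Rule | Trigger, normal baseline | Trigger, abnormal baseline | Action |
|---|---|---|---|
| Appendix G, row 1 | AST/ALT >3×ULN and/or TB >1.5×ULN as printed (doubtful, see below) | AST/ALT 1.5–3.0×baseline and/or TB >1.0–1.5×baseline | No dose change |
| Appendix G, row 2 | AST/ALT >3–5×ULN and/or TB >1.5–3.0×ULN | AST/ALT >3–5×baseline and/or TB >1.5–3.0×baseline | Hold, then resume after improvement and steroid taper |
| Hy's law bullet (in the row 3 cell) | AST/ALT >3×ULN plus TB >2×ULN, no initial cholestasis, no alternative cause | Same, in ULN | Permanent discontinuation |
| Section 10.8.2 | ALT/AST >3×ULN with TB >2×ULN, no definitive diagnosis | Same, in ULN | Interrupt; silent on restart |

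**Normal baseline.** Take ALT 4×ULN and TB 2.5×ULN, no cholestasis, no other cause.
- Row 2: 3 < 4 ≤ 5 and 1.5 < 2.5 ≤ 3.0, so hold and later resume. The row carries no Hy's law exception.
- Hy's law bullet: 4 > 3 and 2.5 > 2, so permanent discontinuation.
- Section 10.8.2: same thresholds, so interrupt.

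The clash between resuming and stopping permanently covers the whole band of ALT/AST >3–5×ULN with TB >2–3×ULN. It does not depend on how row 1 is read. By contrast, ALT 4×ULN with TB 1.8×ULN meets row 2 but neither Section 10.8.2 nor Hy's law, so the clash begins only once TB passes 2×ULN.

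**Abnormal baseline.** Inclusion criterion 11 allows AST/ALT up to 2.5×ULN (5×ULN with liver metastases) and bilirubin up to 1.5×ULN. Take baseline ALT 2×ULN and TB 1.5×ULN, rising to ALT 4×ULN and TB 2.2×ULN.
- ALT: 4 / 2 = 2.0×baseline, inside 1.5–3.0.
- TB: 2.2 / 1.5 = 1.47×baseline, inside >1.0–1.5.
- Both values fall in row 1 and in no higher row, so no dose change.
- In ULN, 4 > 3 and 2.2 > 2. The Section 10.8.2 threshold is met, and so is the Hy's law threshold if there is no cholestasis or other cause.

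This window is narrow. Row 1 ends at 1.5×baseline for TB, so passing 2×ULN inside it needs a baseline above 2 / 1.5 = 1.33×ULN. With entry capped at 1.5×ULN (confirmed Gilbert's syndrome is exempt), the highest row 1 value is 1.5 × 1.5 = 2.25×ULN. Both ALT/AST and TB must be abnormal at baseline; otherwise the normal one, measured in ULN, lands in row 2 or above.

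**Row 1, normal baseline.** The printed trigger is "AST or ALT $> 3 \times$ ULN if baseline normal". Read literally, it overlaps row 2, and a result such as ALT 2.5×ULN with TB 1.2×ULN falls in no row. The abnormal-baseline bands in the same cell sit directly below those of row 2, and worsening leads to the next row. A lost or inverted sign is likely. Nothing above relies on this symbol.

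**The case against.** The best defence is that the rules form a sequence. Interrupting and holding are the same immediate act. Section 10.8.2 governs the time while the cause is unknown, and Hy's law can be declared only after cholestasis and other causes have been excluded, which cannot be known at the first draw. The bullet also speaks of any case and states thresholds below those of its row, so it can be read as reaching across the table.

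Much of this stands. Interrupt against hold is no conflict, and interruption followed by permanent stop is coherent. What the defence does not supply is a statement that the Hy's law bullet overrides the resume instruction in row 2, or any text on restart in Section 10.8.2. Nor does it touch the abnormal-baseline mismatch, which comes from different units.

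A reader might go further and infer that one result meets four conflicting rules, so that a patient can stay on drug without a break by following the plan. The documents do not support that. With normal baseline, the no-change limb rests on one doubtful symbol in row 1. With either kind of baseline, Section 10.8.2 still requires interruption when no diagnosis is established.

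**Conclusion.** The plan is wrong as written on two counts. With normal baseline, row 2 and the Hy's law bullet give opposite instructions on restarting drug for ALT/AST >3–5×ULN with bilirubin >2–3×ULN, no cholestasis and no other cause. With abnormal baseline, the no-change row can apply to a result that meets the interruption threshold and possibly the permanent-stop threshold. No passage gives precedence. The firm risk in the first case is resumption after a hold; in the second it is a missed interruption at a site that consults only the table.

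The number of patients affected cannot be derived. A reader might apply the 15.5% hepatic-event rate quoted in Section 1.3.2.3 to the 27 Phase II patients (0.155 × 27 = 4.2). That rate counts hepatic events of any kind, in a durvalumab plus tremelimumab pool; the pattern at issue is a subset for which the documents give no rate. The case for correction rests on the contradiction in dosing rules and its safety bearing, not on frequency.

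The conclusion takes the row 2, Hy's law and abnormal-baseline thresholds as printed.

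**What to change.** The clinical team must reconcile Section 10.2.1, Section 10.8.2 and the Appendix G hepatitis rows so that, for normal and for abnormal baseline, each combination of ALT/AST and bilirubin leads to one action. The text should state which rule takes precedence, whether the Hy's law rule applies across all rows, and what Section 10.8.2 intends on restart. It should also settle how thresholds in multiples of ULN and of baseline work together. The normal-baseline trigger in row 1 should be checked against the source document and corrected if the sign is wrong. We take no view on which clinical action is right. The cost is a wording amendment to the protocol and Appendix G; no design, sample size or analysis changes.
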